# 6. Study Objectives and Design

## 6.1. Study Objectives

This research aims to elucidate LiOr's plausibility, at a known safe dose, over an extended period in a preliminary study. This is a feasibility study comprising the preliminary work required prior to formal trials examining commercially available LiOr supplementation for DMF. No specific hypotheses are therefore proposed. In this open label study, people who constitute a target population for LiOR will be invited to take commercially available LiOr for up to six months to establish its plausibility as a putative intervention for trials. The specific objectives are to investigate up to six months of open-label 20mg daily LiOr to identify its within-subjects effects on the following as co-primary outcomes:

1. The potential to examine bioavailability of LiOr (i.e. whether lithium is present at detectable levels in the serum using a standard laboratory lithium test), assessing lithium levels in serum.

2. The acceptability of 20mg daily LiOr over 6 months (assessed by self-report adherence and discontinuation rates) to inform a future study design.

3. Description of any positive and/or negative experiences of 20mg daily LiOr over 6 months (assessed via participant-report) to inform a future study design.

4. The feasibility of the protocol including intervention delivery and assessment visits (including assessments mentioned above, plus putative primary (mood) and secondary (functioning, cognition) outcome measures and assessment of potential confounders). Overall feasibility will be assessed via missing data and study withdrawal rates.

An exploratory analysis of change will be undertaken as secondary objectives for measures over time to inform a future definitive study design:

1. LiOR's biological effects, through assessment of key candidate blood-based biomarkers, namely neuroprotective growth factors (BDNF, VEGF) and inflammatory cytokines (IL-6, TNFa, IL-1b, IL-8, CRP) between week 0 and week 26.

2. LiOr's effects on mood, through assessing changes in mood ratings between week 0 and week 26.

3. LiOr's effects on cognition and functioning, through assessing changes in cognitive and psychosocial function between week 0 and week 26.

These aims will be met via within-subjects comparisons for each timepoint relative to baseline (weeks 2, 4, 8, 16, 26).

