## 7. Study Intervention

#### 7.1. Therapy/Intervention Details

This section relates to the lithium orotate (LiOR) supplementation (N=40). The study will not interfere with usual care in any way, although the study team will inform participants' named healthcare professionals (GPs or secondary care clinician if under outpatient care) of their participation which includes LiOR supplementation. LiOr is available in 5mg, 10mg or 20mg doses. As our previous research has shown that individuals frequently take 20mg LiOR once per day of their own accord, without need for titration, we encourage participants to start from this dose. We do not permit a higher dose, as there is no evidence to date of commercial LiOR supplementation at these doses. We will permit a lower dose, if participants desire: as capsules are 5mg each, participants can select to take fewer capsules daily and we will collect this information. We will measure the rates and duration of doses taken. We will support participants if they have questions. Participants will receive bottles/pots as can be purchased, which contain 60 x 5mg capsules (which covers up to 20mg per day for 15 days). Between weeks 0 -2, and 2 – 4, one supply can be provided at the earlier time until the upcoming visit. Subsequently, or if visits are not conducted within 15 days (i.e., participants would otherwise have depleted supply), the next supply of LiOR will be delivered via special delivery Royal Mail with receipt confirmed. This will be undertaken on the basis of checking with participants regularly the quantity of LiOR they have remaining to ensure a continual supply. At the 26-week assessment, participants will be asked to return any remaining LiOR. The lithium orotate purchased is manufactured by Swanson www.swanson.co.uk. [name] team at Newcastle University have examined the quantity and consistency (both within and between batches) determining these to be accurate and stable. Swanson have provided King's Clinical Trial Unit with quality documents (including demonstration of quality, purity and potency at the point of release of the product onto the market, and over-time). These were reviewed by the CTU's pharmacist who has confirmed appropriateness for progressing in the study with these. The supplement will be purchased directly from the supplier and stored in locked cupboards, in a locked office at King's College London, that only the research team will have access to. These will be a cool, dry place as per manufacturer instructions and we will ensure that the product expiry date outlives the date to participants' next supply date. Records will be kept of distribution to participants as per above. The products will not be unsealed or altered in any way before distribution to participants.

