#### 7.3. Intervention adherence

Adherence will be examined via completion of the participant-reported, validated Tablets Routine Questionnaire. A TRQ score equating to 80% adherence is a conservative threshold for dichotomous adherence definition. (see Section 10 for more details).

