#### Screening session

Usually conducted over the phone by a trained researcher, or if potential participants are willing, by videocall (i.e., King's College London MS Teams) study information will be discussed and verbal consent for screening obtained. Verbal consent for screening will be recorded in a secure, password-protected spreadsheet for all potential participants. If the potential participant is willing, screening will provide an initial determination of eligibility. Specifically, eligibility will be assessed via screening procedures as follows:

- Open questions for self-report:
  - Eligible age range.
  - Willingness to try a commercially available lithium supplement.
  - Clinical health diagnoses (including bipolar disorder).
  - Severity of any diagnoses [participants are excluded if admitted to hospital within the past 6 months, have a planned admission in the upcoming 6 months, or attend outpatient/secondary services for an illness other than an affective disorder at least once per month].
  - Current treatments undergone for depression [name(s) of current medication, initiation / withdrawal and historical dose changes].
  - Ineligibility for lithium [as above; taking lithium, known cardiac disease or insufficiency, renal impairment, untreated thyroid dysfunction, breastfeeding, pregnancy, hyponatraemia, dehydration, regular use of NSAID, ACEI or diuretics, psoriasis, Addison's disease, Brugada syndrome or family history of Brugada.]
  - Ability to travel to one of the research sites on a regular basis over 6 months.
- MINI interview, MDD module, to establish current depressive episode and suicide module to establish nonsignificant suicide risk.
- (if not completed within Qualtrics within the last week), Internal States Scale [ISS] to establish presence of mixed features within current depressive episode.
- Ability to communicate fluently in English: researcher-defined, via ability to communicate during discussions about understanding of participant information and prior questions.
- Ability to provide informed consent to participate: researcher-defined, via communications and understanding of the procedures being consented to.

If inclusion criteria are met following this, the W0 assessment will be scheduled.

All assessments are expected to take place in the morning, as (post-LiOR initiation), blood samples are taken in the morning, at least 12 hours after the last LiOR dose, to avoid acute effects of lithium intake.

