#### W0: Baseline Assessment

Before the assessment begins, written informed consent will be completed by the participant. The following measures will then be administered.

Blood test

• 2 x tube serum for the detection of lithium levels, using a standardized validated assay, with a lower limit of detection of 0.1mmol/L and candidate inflammatory markers and growth factor proteins.

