#### Sociodemographic/illness-history/service use questions

- Date of birth, gender, ethnicity, height, weight, education level (highest level of education), employment status, substance use (e.g., smoking, alcohol), stressful life events within the past 12 months [baseline only]
- Current health symptoms [week 0 and 26]
- Current pharmacological or other medical treatments (type, dose, frequency of use, duration of use) [all timepoints]
- Previous use of lithium [baseline only]
- Use of healthcare and related services [week 0 and 26]
- Psychiatric comorbidities (questions) [week 0 and 26]
- Bipolar risk measures (questions; MINI bipolar section, HCL, TEMPS) [week 0 and 26]

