#### Wellbeing measures

- Low mood: The Maudsley 3-item visual analogue scale (M3VAS) and investigator-rated Inventory of Depressive Symptoms (IDS) [all timepoints]
- Anxiety: The Generalised Anxiety Disorder 7-item scale (GAD7) [all timepoints]
- Elevated mood: The internal states scale (ISS) and investigator rated Young Mania Rating Scale (YMRS) [all timepoints]
- Functional/wellbeing measures [EQ5D[week 0 and 26], FAST[all timepoints]]

Participants will, at the end of the assessment, be provided with one pot containing 60 LiOR capsules (for weeks 0 to 2). They will also be provided with an information sheet regarding LiOr, and instructed to begin taking the supplement the next day and once each day thereafter.

The researcher will offer two aids to help participants remember to take the supplement: participants can choose to receive a daily text message from the team to remind them to take their daily LiOR, or they can (along with the researcher if desired) set themselves an alarm/reminder for themselves.

The researcher will subsequently send a letter of notification regarding the study (and information about LiOR) to the participants' named Healthcare Professional.

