## 12.2. Analysis

Intention-to-treat analyses will be undertaken. In a few cases, a sensitivity analysis will be carried out, excluding non-adherent participants (these are specified below, where this applies).

Final analyses will be conducted after data collection has been completed and data cleaned. However, it is worth noting that an interim analysis is planned in May 2025 for all primary analyses below. This is for the purpose of initial pilot data to be included in funding applications being submitted for a feasibility study. No changes to the protocol or any procedures will be made based on this.

Variables will be summarised using descriptive statistics (i.e., mean and standard deviation [SD] or median and interquartile range [IQR] or frequencies and proportions, as appropriate).

Analyses pertaining to each outcome are listed below:

1. LiOR bioavailability as assessed by lithium levels in serum. This will be analysed descriptively, as above. Intraand inter- participant variation will be calculated. Overall changes over time may be assessed using a repeatedmeasures ANOVA (including only adherent participants taking a stable dose) to inform a potential future trial design.

2. LiOR acceptability as assessed by adherence rates (TRQ) and discontinuation. Rates of adherence (< 20% missed) will be assessed descriptively for each timepoint, and extent of adherence will also be described as a continuous (total TRQ score) measure. Rates of discontinuation (participant-report) will be described. Continuous adherence scores (for participants not discontinuing LiOR) over time will be tentatively compared using a repeated-measures ANOVA to inform a potential future trial design.

3. Subjective experiences of LiOR: negative experiences will be described via continuous LiSERS score measure, and positive experiences will be reported as participant-reported rates (yes/no to those listed). LiSERS scores over time (adherent participants only) will be compared using a repeated-measures ANOVA (possibly including dose as a between-subjects factor, pending dose variation within and between participants) to inform a potential future trial design.

4. Protocol feasibility as assessed by the rates (assessed descriptively) of attrition from the study, and of visits missed, and specific data for the putative primary outcomes i.e., mood measures.

There are three secondary outcomes, analysed as exploratory indications of change to inform a future definitive study design:

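### Time from last dose to blood draw has a 12-hour minimum only, and the protocol does not require dose time to be recorded, so the lithium co-primary cannot be read by time since dose

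*Protocol*

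**What the plan says.** **Sampling rule.** The protocol's rule on timing is in Section 10.1 (Screening session): "blood samples are taken in the morning, at least 12 hours after the last LiOR dose". Section 10.2 refers blood collection to local procedures and gives no interval.

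**Dosing.** Section 10.1 (Wellbeing measures) has participants "instructed to begin taking the supplement the next day and once each day thereafter". No time of day is fixed. A daily text message or the participant's own alarm is offered as a reminder, also without a stated time.

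**What is recorded about doses.** Section 7.1: "We will measure the rates and duration of doses taken". Section 10.1 lists "Current pharmacological or other medical treatments (type, dose, frequency of use, duration of use) [all timepoints". Section 7.3: "Adherence will be examined via completion of the participant-reported, validated Tablets Routine Questionnaire". None of these items is described as the time of the last dose or the interval from dose to draw.

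**Outcome and analysis.** Section 6.1 defines co-primary 1 as "whether lithium is present at detectable levels in the serum using a standard laboratory lithium test". The assay is one "with a lower limit of detection of 0.1mmol/L" (Section 10.1, W0). Section 12.2 describes the levels, says that intra- and "inter- participant variation will be calculated", and allows an optional repeated-measures ANOVA limited to adherent participants on a stable dose. Time since dose is not mentioned.

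**The concern.** With a minimum and no maximum, the interval depends on the participant's habit. Someone who takes the capsules in the evening meets the rule at about 12 hours. Someone who takes them in the morning, and holds that day's dose until after the draw, meets it at about 24 hours. After a missed dose the gap is longer still. Participants who discontinue are asked back for week 26 (Synopsis), where all outcome measures are repeated, so a sample taken long after stopping also satisfies the rule.

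This matters because the outcome is read against a fixed limit. If typical levels were far from 0.1 mmol/L, a difference of 12 hours would change little. If they lie close to it, the share of samples called detectable depends partly on when people happen to take the capsules. The same delay enters the variation estimates: as between-participant variation if each person keeps a steady habit, and as within-participant variation if habits shift between visits. These estimates are meant to inform a later trial. An analysis plan can deal with this only if dose time was collected.

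**Working it through.** **1. The plan's own ratio.** Section 11.1 puts the prescribed dose at roughly 6 to 8 times the elemental lithium in 20 mg. Section 5 gives more than 112 mg of ionic lithium for the prescribed range, taken here as the 600 mg end. Then 112 / 20 = 5.6, and at 800 mg 5.6 × 800 / 600 = 7.5. These round to 6 and 8, so the stated ratio reproduces.

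**2. Implied level on 20 mg.** Inputs from Section 11.1: 0.6 to 0.8 mmol/L at 600 to 800 mg carbonate. Formula: reference level / ratio, with matched ends.

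- Stated ratio: 0.6 / 6 = 0.100; 0.8 / 8 = 0.100.
- Ratio from step 1: 0.6 / 5.6 = 0.107; 0.8 / 7.5 = 0.107.

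The implied level is about 0.10 to 0.107 mmol/L. This assumes dose proportionality, that orotate behaves like carbonate, and that 0.6 to 0.8 mmol/L is a 12-hour level. The protocol states none of these.

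**3. Effect of delay.** Formula: level at 24 h = level at 12 h × 0.5^(12 / half-life). The half-life is an assumption.

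| Assumed half-life | 24 h as fraction of 12 h | From 0.100 | From 0.107 |
|---|---|---|---|
| 18 h | 0.63 | 0.063 | 0.067 |
| 24 h | 0.71 | 0.071 | 0.076 |
| 36 h | 0.79 | 0.079 | 0.085 |

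Every 24-hour value is below 0.1 mmol/L.

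**4. Share detectable.** Further assumption: log-normal levels with a between-participant CV of 20% to 40% and median m. Formula: share = 1 − Φ(ln(0.1 / m) / s), with s = √ln(1 + CV²). For example, m = 0.107 and CV 20% give s = 0.198 and a share of 63%.

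- At 12 h, m = 0.100 to 0.107: 50% to 63% detectable.
- At 24 h, same people, half-life 18 to 36 h: 1% to 34% detectable.

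**5. Apparent variation from delay alone.** On the log scale, SD = (ln 2 / half-life) × SD of delay, and CV = √(exp(SD²) − 1).

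- Delays uniform over 12 to 24 h (SD 12 / √12 = 3.46 h): CV 13%, 10% and 7% for half-lives of 18, 24 and 36 h.
- Half at 12 h and half at 24 h (SD 6 h): CV 23%, 17% and 12%.

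**6. Sensitivity to the starting level.** Crossing the ends of Section 11.1's ranges gives 0.6 / 8 = 0.075 and 0.8 / 6 = 0.133. At 0.075 a sample is already below the limit at 12 h. At 0.133 the 24-hour value is 0.133 × 0.63 = 0.084 to 0.133 × 0.79 = 0.105, so with a 36-hour half-life the typical value stays just above the limit. The share detectable still falls, from 77%–93% at 12 h to 19%–61% at 24 h.

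**The case against.** Several points on the other side carry weight.

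- **Dose time may be captured anyway.** Staff who apply the 12-hour minimum must find out when the last dose was taken, and a case report form or local procedure not shown may have a field for it. A reader might infer that dose time goes unrecorded; the document supports only that the protocol does not require it.
- **There is a practical ceiling.** A reader might infer that the interval is unbounded. For an adherent once-daily participant sampled in the morning it is about 24 hours. Reminders favour a regular habit, which would limit the within-participant part. This leaves the 12-to-24-hour spread between participants untouched, and the restriction to adherent, stable-dose participants applies only to the optional ANOVA.
- **Section 11.1 does not predict a level.** It gives the 6 to 8 ratio to explain why exceeding 0.6 mmol/L would be unexpected. The 0.10 to 0.107 figure is a derivation under the assumptions in step 2, not the protocol's claim.
- **Self-managed use is a fair setting.** Detectability at the times people actually take the supplement is a legitimate question, and a narrow window would lose samples from a study of 40. That argues against discarding samples, not against recording their timing.
- **Windows and adjustment belong to an analysis plan.** This is true of the analysis, but that plan cannot recover a dose time that was never collected.
- **The assay limit may matter more.** By the same scaling, the permitted 15 mg dose implies 0.075 to 0.080 mmol/L even at 12 hours, and 10 mg and 5 mg imply less. This stands; timing is one constraint on co-primary 1, not the only one.

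**Conclusion.** The point holds as a cheap improvement. As written, the protocol lets samples from about 12 to about 24 hours after dosing, and some later, be described together for an outcome read against 0.1 mmol/L, without requiring the information needed to tell them apart.

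The direction is firm: after 12 hours, a longer delay lowers the level. The size rests on the scaling assumptions, the half-life and, for the shares detectable, the CV. None of these is in the documents. A reader might infer that every 24-hour sample would read undetectable, or that co-primary 1 is invalid. The documents support neither: higher starting levels can stay above the limit, and the outcome is descriptive, with no hypothesis, success threshold or error rate. What is at risk is the interpretation of the detectable share and of the variation estimates carried into a later trial.

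**What to change.** At every post-baseline visit, record the date and time of the last capsule and the date and time of the blood draw. In the description of co-primary 1, report detectability by time since dose, for example near 12 hours versus near 24 hours or later, and show samples taken after discontinuation separately. Include hours since dose when estimating intra- and inter-participant variation.

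No sample need be dropped and no dosing rule changes. The cost is a small addition to the case report form and slightly more analysis. The time of the last capsule would be self-reported, and with at most 40 participants the subgroups by time since dose will be small.

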#### W0: Baseline Assessment

Before the assessment begins, written informed consent will be completed by the participant. The following measures will then be administered.

Blood test

• 2 x tube serum for the detection of lithium levels, using a standardized validated assay, with a lower limit of detection of 0.1mmol/L and candidate inflammatory markers and growth factor proteins.

#### Sociodemographic/illness-history/service use questions

- Date of birth, gender, ethnicity, height, weight, education level (highest level of education), employment status, substance use (e.g., smoking, alcohol), stressful life events within the past 12 months [baseline only]
- Current health symptoms [week 0 and 26]
- Current pharmacological or other medical treatments (type, dose, frequency of use, duration of use) [all timepoints]
- Previous use of lithium [baseline only]
- Use of healthcare and related services [week 0 and 26]
- Psychiatric comorbidities (questions) [week 0 and 26]
- Bipolar risk measures (questions; MINI bipolar section, HCL, TEMPS) [week 0 and 26]

#### Cognitive measures

 Digital THINC-IT battery including validated tests of processing speed and attention, memory, executive function and subjective cognitive functioning [Spotter (Choice Reaction Time), Symbol Check (1-back test), Trails (Trails Making Test B), and Codebreaker (Digit Symbol Substitution Test), Perceived Deficit Questionnaire, 5-item) [all timepoints].

#### Wellbeing measures

- Low mood: The Maudsley 3-item visual analogue scale (M3VAS) and investigator-rated Inventory of Depressive Symptoms (IDS) [all timepoints]
- Anxiety: The Generalised Anxiety Disorder 7-item scale (GAD7) [all timepoints]
- Elevated mood: The internal states scale (ISS) and investigator rated Young Mania Rating Scale (YMRS) [all timepoints]
- Functional/wellbeing measures [EQ5D[week 0 and 26], FAST[all timepoints]]

Participants will, at the end of the assessment, be provided with one pot containing 60 LiOR capsules (for weeks 0 to 2). They will also be provided with an information sheet regarding LiOr, and instructed to begin taking the supplement the next day and once each day thereafter.

The researcher will offer two aids to help participants remember to take the supplement: participants can choose to receive a daily text message from the team to remind them to take their daily LiOR, or they can (along with the researcher if desired) set themselves an alarm/reminder for themselves.

The researcher will subsequently send a letter of notification regarding the study (and information about LiOR) to the participants' named Healthcare Professional.

#### W2: Intermediary assessment:

- Blood test (repeat from baseline)
- Cognitive test (repeat from baseline)
- Wellbeing measures (repeat from baseline)
- Adherence: Tablets Routine Questionnaire (TRQ) [all remaining timepoints]
- Subjective effects of LiOR: Lithium Side Effects Rating Scale (LiSERS) modified to bolster both positive and negative effects of lithium [all remaining timepoints]

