#### 6.3. Study Flowchart

Table 1: Summary of study procedures and measures.

Procedures/Measures	Screening	Baseline (W0)	Intermediary (W2, 4, 8, 16)	Follow-up (W26)
Eligibility assessment [questions, MINI suicide, bipolar, & MDD  ,	Х			
Informed consent		Х		
LiOr provision		Х	Х	
Patient information	Х			
Sociodemographic		Х		х
Illness history [questions, HCL  , TEMPS 16* ]		Х		
Service use and health-related quality of life (EQ5D) 		Х		Х
Cognitive battery (THINC-IT  )		Х	Х	Х

Procedures/Measures	Screening	Baseline (W0)	Intermediary (W2, 4, 8, 16)	Follow-up (W26)
Mood self- (ASRM  / M3VAS  / GAD7  / ISS  ) & investigator- report (IDS  / YMRS 		Х	Х	х
Functioning [FAST  ]		Х		Х
Blood test	Х	Х	Х	Х
Subjective experiences (LiSERS  )			Х	Х
Adherence (TRQ  )			Х	Х

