
#### 7.2. Intervention timeline

The intervention will begin at the start of Week 1, the day after baseline assessment. The intervention will continue for 6 months, until the final assessment at week 26, or as long as participants are willing to continue with the intervention during this time.

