## 9. Selection and Withdrawal of Participants

#### 9.1. Inclusion Criteria

Participants will be:

1) Aged between 18-65 at study entry.

2) Meet DSM-5 criteria for a current depressive episode (MINI) and exceed thresholds indicating presence of mixed features (Internal States Scale; ISS).

3) Undergoing stable pharmacological treatment for depression (intervention/dose unchanged for >6 weeks).

- 4) Willing to try a commercially available lithium supplement.
- 5) Willing to attend planned study visits.

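### LiSERS, the only scale named for co-primary objective 3, is first given after LiOr has started, so complaints already present cannot be separated from LiOr effects unless its items ask about attribution

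*Protocol*

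**What the plan says.** Protocol section 6.1 sets out to "identify its within-subjects effects on the following as co-primary outcomes". The third item on that list is "Description of any positive and/or negative experiences of 20mg daily LiOr over 6 months (assessed via participant-report". After the secondary objectives the section closes with "These aims will be met via within-subjects comparisons for each timepoint relative to baseline (weeks 2, 4, 8, 16, 26".

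The row "Subjective experiences (LiSERS" in Table 1 (section 6.3) is marked for the intermediary visits and W26 only. Section 10.1 does not list the scale among the W0 measures. It introduces LiSERS at W2, "modified to bolster both positive and negative effects of lithium [all remaining timepoints". Section 7.2 fixes the start of LiOr: "The intervention will begin at the start of Week 1, the day after baseline assessment".

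Section 12.2, item 3, gives the analysis: "negative experiences will be described via continuous LiSERS score measure, and positive experiences will be reported as participant-reported rates". It adds a repeated-measures ANOVA of LiSERS scores over time in adherent participants. No other scale is named for this objective.

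**The concern.** The study has one arm and no blinding, so the only internal reference for a symptom reported on LiOr is the same person's report before LiOr. Everyone enrolled is in a depressive episode with mixed features and meets the criterion "Undergoing stable pharmacological treatment for depression (intervention/dose unchanged for >6 weeks". Complaints of the kind a side-effect scale lists may well be present before the first capsule.

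If the LiSERS items record what is present, the raw scores and yes/no rates in section 12.2 mix that background with whatever is new. This affects negative and positive experiences alike. The results are meant to inform the design of a later trial, so a background complaint read as an effect of LiOr, or an early effect read as no change, would carry forward. A pre-dose value that was never collected cannot be recovered by any later analysis.

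**Working it through.** The plan gives no figure for LiSERS. Its one precision figure, ±15 points for a 50% dropout rate with 40 participants (section 12.1), reproduces as 1.96 × √(0.5 × 0.5 / 40) = 0.155. It does not bear on this point.

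**1. Visits against the start of LiOr**

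| Visit | LiOr started? | LiSERS planned? |
|---|---|---|
| W0 | no | no |
| W2, W4, W8, W16, W26 | yes | yes |

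LiSERS therefore has 0 values before the start and 5 after it. Section 12.1 counts six repeated measures; for LiSERS there are five. Of the five possible comparisons with baseline (W2, W4, W8, W16 and W26, each minus W0), none can be made.

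**2. What the ANOVA can see**

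Write the mean score at visit j as b + d(j), where b is the background present before LiOr and d(j) is whatever has been added by visit j. The time effect is built from contrasts whose weights sum to zero over the five visits, so b drops out. So does any part of d(j) that is the same at all five visits. An effect that appears in the first fortnight and stays level adds the same amount to all five means and shows as no change over time. Only movement after W2 is visible.

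**3. What the raw rates can see (illustration; these prevalences are assumed, not taken from the Protocol)**

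Suppose an item records presence, a proportion p already has the symptom and keeps it, and a proportion q of the rest develop it by W2. The observed W2 rate is p + (1 − p) × q.

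- With q = 0 and p = 0.10, 0.30 or 0.50, the number reporting it among 40 is 4, 12 or 20, although LiOr caused none.
- With q = 0.10 the rates are 0.10 + 0.90 × 0.10 = 19%, 0.30 + 0.70 × 0.10 = 37%, and 0.50 + 0.50 × 0.10 = 55%.
- The 37% also arises from p = 0.10 and q = 0.30: 0.10 + 0.90 × 0.30 = 37%. One observed rate fits both a mostly background and a mostly new picture, and without W0 the data cannot choose between them.

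**4. Whether other W0 data fill the gap**

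Section 10.1 has a general question on current health symptoms at W0 and W26. It is not LiSERS, is not asked at W2 to W16, and section 12.2 does not link it to LiSERS. Mood, anxiety and perceived cognitive deficit are measured at W0 and every later visit, but on other scales. None gives an item-by-item reference for LiSERS.

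**The case against.** Four stronger readings are tempting. The documents do not support them.

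- **That the schedule plainly breaches section 6.1.** The sentence on comparison with baseline directly follows the secondary objectives and may mean only those. It cannot literally cover every co-primary objective, because adherence, discontinuation and withdrawal have no baseline value. Objective 3 is worded as a description, section 6.1 proposes no hypotheses, and section 12.2 does not promise LiSERS change from baseline. What remains is tension with the lead-in on within-subject effects, and an ANOVA that goes beyond description.
- **That pre-existing symptoms will be counted as LiOr effects.** The modified items are not shown. Section 10.1 labels the scale as subjective effects of LiOr. If items ask what the participant attributes to the supplement, some background complaints would be left out, and a W0 form in the same words would have no meaning. This limit stands. Attribution by unblinded participants still does not replace a pre-dose measurement.
- **That nothing is known about symptoms before LiOr.** The W0 mood, anxiety and cognition measures, the record of current treatments and the general symptom question all give some background. Adverse events are also asked about at each visit and assessed for relatedness (section 11.3). These soften the gap without closing it, above all for physical complaints.
- **That a W0 score would bring a known gain in precision.** No correlation between visits is given. For a simple change score with equal variances, the variance is 2(1 − r) times that of a single visit, which at r = 0.5 is 1.0 and so no gain. The case rests on having a reference, not on precision.

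The late start of the adherence questionnaire is not a parallel fault: adherence has no meaning before LiOr begins, whereas symptoms do.

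**Conclusion.** The point holds in a limited form. The timing is certain: LiSERS has no pre-dose value, none of five baseline comparisons is possible, and the planned ANOVA cannot detect an effect already present by W2. That pre-existing complaints cannot be separated from LiOr effects is conditional. It holds to the extent that items record symptoms present and not symptoms attributed to LiOr, and the Protocol does not settle which. The size of any misattribution cannot be stated, because no symptom rates are given. Confidence is moderate.

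This is a design weakness that should be mended, and it sits badly with the lead-in to section 6.1. It is not a proven contradiction. A W0 value would show which complaints are new or worse; without a control group it would still not prove that LiOr caused them.

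**What to change.** - Give the LiSERS item list, including the added positive items, at W0 before the first capsule. Word the items as symptoms or experiences present now, and use the same wording at every later visit; otherwise the W0 form is a different instrument.
- Mark it under Baseline in Table 1 and add it to the W0 measures in section 10.1.
- In section 12.2, item 3, report change from W0 and the proportion of participants with each item new or, where the item is graded, worsened.
- In section 6.1, state which objectives the comparison with baseline covers.

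The cost is one more questionnaire at a visit that already takes place, and possibly rewording the modified items at all visits. If the sponsor prefers attribution wording and no W0 form, the Protocol should say that objective 3 is purely descriptive and outside the baseline comparison. That would settle the wording but would not supply the missing reference.
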